8.2 Secondary objectives

- To investigate safety and clinical parameters of somapacitan treatment in paediatric patients with GHD in the setting of routine clinical practice.
- To compare the occurrence of AEs, SAEs, serious ADRs including neoplasms and T2DM in patients treated with somapacitan with historical data from literature (NordiNet® IOS, ANSWER studies and GeNeSIS registry) paediatric GHD patients treated with daily somatropin.

 Protocol
 Date:
 17 July 2024
 Novo Nordisk

 Study ID: NN8640-4787
 Version:
 3.0
 Status:
 Final

Page:

18 of 48

[figure not shown]
9 Research methods

9.1 Study design

EU PAS No.: Pending

This is a non-interventional, multi-national, single-treatment arm, observational, registry-based study to investigate the long-term safety and clinical parameters of somapacitan in paediatric patients with GHD under routine clinical practice conditions. The study design is shown schematically in Figure 9-1.

Figure 9-1 Schematic diagram of the study design

Abbreviations: GHD = growth hormone deficiency, FPFV = first patient first visit, LPFV = last patient first visit, and LPLV = last patient last visit.

The study population will consist of at least 400 paediatric GHD patients from the GloBE-Reg registry treated with once-weekly somapacitan and fulfilling the eligibility criteria of the present study (see Sections 9.2.2 and 9.2.3). The total duration of the study is planned for 10 years consisting of a 5-year recruitment period in the registry followed by a follow-up period of at least 5 years. Individual patients will be followed up from inclusion into GloBE-Reg until last routine visit within the full study duration, i.e. individual follow-up time is expected to be above 5 years. Patient data are planned to be collected beyond the age of 18 years and irrespective of discontinuation of somapacitan. The main purpose of this study is to observe patients for long-term safety. The planned study duration is from Q4 2024 until Q4 2034.

9.1.1 Endpoint(s)

The primary endpoint of this study is to report all ADRs from baseline (week 0) to EOS (up to 10 years) to investigate the long-term safety in paediatric patients with GHD under routine clinical practice conditions.

The secondary endpoints and clinical parameters are described in Section 9.3.

External comparators:

The combined data from NordiNet[®] IOS and ANSWER will be used as an external comparator for the occurrence of ADRs and neoplasms, and data from the GeNeSIS study will be the external comparator for incident T2DM.

• The NordiNet® and ANSWER studies evaluated the safety of GH treatment as frequency and incidence rates of SAEs and/or treatment-related AEs including incidence rates of neoplasms. Both studies evaluated the safety of real-world treatment with Norditropin® for

Protocol		Date:	17 July 2024 Novo Nordisk
Study ID: NN8640-4787	CONFIDENTIAL	Version:	3.0
UTN: U1111-1294-5941	CONFIDENTIAL	Status:	Final
EU PAS No.: Pending		Page:	19 of 48

the indications requiring GH therapy according to normal clinical practice and treating physicians' discretion, including several paediatric indications including GHD. 6-8

• The GeNeSIS diabetes study included 11,686 GH-treated patients of which, baseline diabetes prevalence was evaluated from a cohort of 8,568 patients (3,368 in the US) who were GH-naïve at study entry. Prevalence and incidence (by SIR) were compared with results from patients aged less than 20 years in the US SEARCH for Diabetes in Youth study. 9,10

9.1.2 Treatment of patients

Patients will be treated with commercially available somapacitan according to routine clinical practice at the discretion of the treating physician. The decision to treat a patient with somapacitan will be made at the treating physician's discretion prior to, and independently from, the decision to include the patient in the GloBE-Reg registry. Novo Nordisk A/S will not provide any products for included subjects during the conduct of the study.

Data collection for the GloBE-Reg registry will happen in conjunction with the patient's usual visits in the clinic. Additionally, optional visits are allowed per local standard of care.

9.2 Setting

9.2.1 Study population

The planned number of patients to be included is at least 400 (both naïve and non-naïve).

9.2.2 Inclusion criteria

For an eligible patient, all inclusion criteria must be answered 'yes'.

- 1. Treated with commercially available somapacitan according to local practice at the discretion of the physician.
- 2. Primary confirmed diagnosis of GHD as per local practice.
- 3. Male or female below 18 years of age at the time of signing informed consent in the GloBE-Reg.

9.2.3 Exclusion criterion

For an eligible patient, the following exclusion criterion must be answered 'no'.

1. Patients with active malignancy or in treatment for active pre-existing malignancy.

9.2.4 Rationale for selection criteria

The study population comprises all patients eligible according to the inclusion and exclusion criteria for this registry-based study as well as the inclusion and exclusion criteria defined for inclusion in the GloBE-Reg. The eligibility criteria have been kept to a minimum to ensure that the study population will represent the broader real-world population of paediatric patients with GHD treated with somapacitan.

9.2.5 Withdrawal criteria

The patient or/and the legally acceptable representative (LAR) may withdraw the consent at will at any time.

Protocol		Date:	17 July 2024	Novo Nordisk
Study ID: NN8640-4787	CONFIDENTIAL	Version:	3.0	
UTN: U1111-1294-5941	CONFIDENTIAL	Status:	Final	
EU PAS No.: Pending		Page:	20 of 48	

GloBE-Reg is responsible for the data collected from the registered paediatric patients. As per the registry on which this protocol is based, there are no specific withdrawal criteria outlined for the patients.

The patient/LAR may choose to withdraw from the registry at any point during the study at the discretion of the local treating physician. Any data that has been processed by GloBE-Reg and has already been shared with the treating physician will be marked as 'deleted case from Registry' so that it is not shared with anybody else or re-used. However, these data will still be retained in case they are required in the future for regulatory purposes.

If the participant withdraws consent, Novo Nordisk A/S may retain and continue to use any data collected before such a withdrawal of consent for the purpose of the study or scientific research. Withdrawals from GloBE-Reg would therefore only affect subsequent data extractions for the study. Therefore, the patient will be regarded as lost to follow-up from the date of last data entry in the latest extract of study data from GloBE-Reg before the date of withdrawal.

9.2.6 Visit procedures

No study-related activities (study-related activities are any procedure related to recording of data according to the protocol) may take place before signed informed consent is obtained.

Data collection for the GloBE-Reg registry will happen in conjunction with usual visits in the clinic. As the data for this study will be drawn directly from GloBE-Reg, the visit procedures are not in the scope of this protocol.

9.2.6.1 Study flow chart

Not included.

9.2.6.2 **Study visits**

Long-term safety and clinical parameters of somapacitan in paediatric patients with GHD will be investigated under routine clinical practice conditions.

9.2.7 Assessments for safety and clinical parameters

Safety Assessment

- **Primary endpoint:** Number of ADRs (from baseline [week 0] to EOS)
- Secondary endpoints: AEs, SAEs, serious ADRs, medication errors, incident neoplasm and incident T2DM from baseline (week 0) to EOS will be assessed.

Note: The EOS will differ from patient to patient.

Clinical parameters

For the list of clinical parameters, see Section 9.3.2.2.

9.2.8 Other assessments

Not applicable.

 Protocol
 Date:
 17 July 2024
 Novo Nordisk

 Study ID: NN8640-4787
 Version:
 3.0

 UTN: U1111-1294-5941
 Status:
 Final

Page:

21 of 48

9.3 Variables

EU PAS No.: Pending

9.3.1 Exposure

- Start date of somapacitan treatment
- Initial dose of somapacitan treatment
- Change of dose (date and new dose)

9.3.2 Endpoints and outcomes

9.3.2.1 Primary endpoint

Table 9-1 Safety parameters (primary endpoints)

Endpoint title	Time frame	Unit
	From baseline (week 0) to EOS ^a (up to 10 years)	Count

^aEOS will differ from patient to patient

Abbreviations: ADR = adverse drug reaction, EOS = End of study

9.3.2.2 Secondary endpoint(s)

Safety

Table 9-2 Safety parameters (secondary endpoints)

Endpoint title	Time frame	Unit
Adverse events (AEs)	From baseline (week 0) to EOS ^a (up to 10 years)	Count
Serious adverse events (SAEs)	From baseline (week 0) to EOS ^a (up to 10 years)	Count
Serious adverse drug reactions	From baseline (week 0) to EOS ^a (up to 10 years)	Count
Number of medication errors	From baseline (week 0) to EOS ^a (up to 10 years)	Count
Incident neoplasm	From baseline (week 0) to EOS ^a (up to 10 years)	Yes/no
Incident T2DM	From baseline (week 0) to EOS ^a (up to 10 years)	Yes/no

^aEOS will differ from patient to patient.

Abbreviations: EOS = end of study, T2DM = type 2 diabetes mellitus.

Clinical parameters

Table 9-3 Clinical parameters (secondary endpoints)

Endpoint title	Time frame	Unit
Height velocity	Yearly	Cm/year
Change in Height Velocity SDS	Yearly	-10 to +10
Change in Height SDS	Yearly	-10 to +10
Change in IGF-I SDS	Yearly ^a	-10 to +10

 Protocol
 Date:
 17 July 2024
 Novo Nordisk

 Study ID: NN8640-4787
 Version:
 3.0
 3.0

 UTN: U1111-1294-5941
 Status:
 Final

Page:

22 of 48

Endpoint title	Time frame	Unit
Change in bone age	Yearly	Years and months
Reaching near adult height ^b	EOS ^b	Yes/no
Change in height SDS in subjects reaching near adult height ^b	From baseline (week 0) to EOS ^c (up to 10 years)	-10 to +10

Note: Near adult height can be defined as: height velocity <2 cm/year over the last 9 months and chronological age >16 years (males) or >15 years (females) or bone age >16 years (males) and > 15 years (females).

EU PAS No.: Pending

Abbreviations: EOS = end of study, IGF-I = insulin-like growth factor 1, SDS = standard deviation score

AEs will be split into all AEs, SAEs and serious ADRs through the evaluation of seriousness and causality entered in GloBE-Reg by the contributing clinics. Seriousness will be categorized into death, life-threatening experience, in-patient or prolongation of existing hospitalization, persistent or significant disability/incapacity or congenital anomaly/birth defect, and important medical event. Causality assessment will be categorized into probable, possible, and unlikely.

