Somapacitan is a long-acting hGH derivative, with a single amino acid substitution in the backbone to which a non-covalent albumin binding moiety has been attached. Somapacitan is intended for once weekly subcutaneous administration with the aim of reducing injection frequency and treatment burden and potentially decreasing the barrier to initiating and/or maintaining replacement therapy in GHD. The mechanism of action of somapacitan is via IGF-I. Daily GH injections can be burdensome for paediatric patients and their caregivers, disrupting and interfering with daily life. This could lead to non-adherence to prescribed replacement therapy and suboptimal clinical outcomes. 3.4

As part of the European marketing authorisation for somapacitan for the treatment of paediatric patients with GHD, Novo Nordisk A/S received a requirement from the Committee for Medicinal Products for Human Use (CHMP) under the European Medicines Agency (EMA) to conduct a non-interventional, observational registry-based study to investigate long-term safety and clinical parameters of somapacitan treatment in paediatric patients with GHD in the setting of routine clinical practice.

As per the RMP, the primary aim of this non-interventional, observational registry-based study is to assess the long-term safety profile of somapacitan with special focus on the important potential risks (neoplasm, T2DM, and medication errors). This post authorisation safety study (PASS) will also provide additional long-term safety information (AEs, SAEs and serious ADRs) and will further substantiate the evaluation of potential risks in relation to treatment with somapacitan.

The secondary aim is to investigate the clinical parameters in patients treated with somapacitan with regards to changes in height velocity SDS, height SDS, IGF-I SDS, and bone age.

To draw clinically relevant conclusions on long-term safety of somapacitan, this study will compare safety data with historical data from literature (NordiNet® IOS, ANSWER⁶⁻⁸ studies and GeNeSIS⁹. 10 registry) of paediatric GHD patients treated with daily somatropin.

Brief description of these external comparators has been outlined below:

NordiNet® IOS (study GHLIQUID-3676) and ANSWER (study HGH-2149)

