9.3.3 Covariates

The following baseline characteristics will be available from the GloBE-Reg data and overlap with the baseline characteristics from NordiNET/ANSWER and GeNeSIS:

- Sex
- Country
- Age at initiation of GH treatment (any GH treatment)
- Duration of GH Treatment at study inclusion (GH naïve or non-naïve patients)
- Height
- Weight
- BMI
- IGF-I
- Bone age
- Medical history of neoplasms
- Medical history of T2DM
- Diabetes risk factors: obesity

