9.7.2.2 Analysis of secondary endpoints

Binary secondary endpoints:

The binary secondary endpoints include:

- Incident neoplasm
- Incident T2DM

Incidence rates will be calculated for both endpoints and compared to aggregated data of incident neoplasms from the combined NordiNET/ANSWER study⁶ and incident T2DM from the GeNeSIS study.⁹ From both studies, the incidence rates for isolated GHD will be used for comparison. The SIR with a 95% confidence interval will be used as an additional estimate for neoplasms and new-onset T2DM.

 Protocol
 Date:
 17 July 2024
 Novo Nordisk

 Study ID: NN8640-4787
 Version:
 3.0
 3.0

 UTN: U1111-1294-5941
 Status:
 Final

Page:

25 of 48

Count-data secondary endpoints:

The analyses of the following secondary endpoints (counted from the baseline (week 0) to the EOS^a) will be done in the same way as the analysis of the primary endpoint:

• Number of AEs

EU PAS No.: Pending

- Number of SAEs
- Number of serious ADRs
- Number of medication errors

Continuous secondary endpoints

For the following secondary endpoints (clinical parameters), the change will be estimated by length of follow up and treatment duration.

- Height velocity
- Change in height velocity SDS
- Change in height SDS
- Change in IGF-I SDS
- Change in bone age

Patients reaching near adult height will be evaluated at EOS only for those who are expected to reach near adult height during the study. Change in height SDS in subjects reaching near adult height will be calculated from baseline (week 0) to EOS.

Note: Near adult height can be defined as height velocity <2 cm/year over the last 9 months and chronological age >16 years (males) or >15 years (females) or bone age >16 years (males) and >15 years (females).

IGF-I SDS will be used to evaluate treatment adherence assuming an increase in IGF-I SDS represents a response to GH treatment.

To deal with patients switching medication in-study and on-treatment analyses will be performed as defined below. The analyses will be repeated separately for GH treatment naïve and non-naïve patients previously receiving other GH treatment as data allows.

In-study

The observation period represents the time frame during which patients are considered to be part of the study, regardless of their adherence to somapacitan treatment. The in-study period starts at the time of informed consent and ends at the date of whichever comes first:

- EOS visit (last visit within the study duration)

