9.9 Limitations of the research methods

Data collection for this study will reflect routine clinical practice rather than mandatory assessments at pre-specified time points. The study captures data in GloBE-Reg from many different regions and settings. As data collection will reflect national, regional, and local differences in routine clinical practice regarding diagnostics, laboratory analyses, and reporting of events, potential issues may arise due to the study design. These issues may result in heterogeneous reporting of specific outcomes and time points for collection. Therefore, it is important to take these differences into account during the interpretation of data.

AEs are collected into GloBE-Reg based on the answer to the below question:

"Since the last recorded clinical encounter in the GloBE-Reg registry, has the patient experienced any untoward medical occurrence (sign, symptom or disease)"

In addition, the physician is responsible for evaluating the seriousness and causality of the AEs.

The safety endpoints are therefore limited to the physician's evaluation of these questions, and due to the secondary collection of data this evaluation cannot be further investigated.

The data source for the study, GloBE-Reg, captures data from many different regions and settings. This leads to a potentially heterogeneous patient population and different local standard of care and data capture, e.g., local differences in diagnostics, laboratory analyses, and reporting of events. This could result in a risk of information bias.

There is a risk of selection bias in the study, affected by the willingness and/or ability of physicians and patients to participate in GloBE-Reg. In addition, any undiagnosed patients will not be able to participate, and the rate of underdiagnosis may vary between regions. This may lead to a selected patient population, which does not accurately reflect the underlying patient population and may result in limited data on certain subgroups.

The long-term follow-up is a strength of this non-interventional study, but also leads to a risk of loss to follow up.

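### Change in bone age, set as a raw yearly change in years and months, is mostly elapsed time and does not separate maturation rate from assessment interval

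*Protocol*

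**What the plan says.** Protocol Section 9.3.2.2, Table 9-3, lists "Change in bone age" among the clinical parameters, with a yearly time frame and the unit "Years and months". The other change endpoints in the table, such as "Change in Height SDS", are on an SDS scale and so are already indexed to age. Height velocity is not an SDS, but it is a rate per year. Bone age is neither age-standardised nor divided by time.

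For the continuous clinical parameters, Section 9.7.2.2 says that "the change will be estimated by length of follow up and treatment duration". Section 9.9 states: "Data collection for this study will reflect routine clinical practice rather than mandatory assessments at pre-specified time points". Section 9.1 describes a "single-treatment arm, observational, registry-based study". Section 9.1.1 names external comparators for ADRs, neoplasms and T2DM, but none for bone age.

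The purpose given in Section 7 is to investigate "changes in height velocity SDS, height SDS, IGF-I SDS, and bone age". Bone age and chronological age appear together only in the note defining near adult height. The protocol defines no difference between them, no ratio and no bone-age SDS for this endpoint.

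**The concern.** Bone age is itself measured on an age scale, so its raw change rises with the calendar in any child who is still maturing. Tabulating that change against length of follow-up and treatment duration, which are both measures of time, builds in a strong positive association. A reader of the report could take it for a treatment effect, although it would appear with no effect at all.

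Irregular assessment dates add a second problem. The raw change is the product of how fast the skeleton matures and how long the gap between assessments was. The endpoint as defined does not say which of the two moved. With no control group and no literature comparator for bone age, the reported number has nothing to be read against.

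**Working it through.** The plan gives no figure for this endpoint, so there is none to reproduce. The check is arithmetic on the definition.

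**Inputs**
- Raw change in years and months, yearly: Table 9-3.
- Individual follow-up expected above 5 years, up to 10: Sections 9.1 and 9.1.1. Intervals t = 1, 5 and 10 years are used.
- Assessment dates not fixed: Section 9.9.
- Maturation rate r, in bone-age years gained per calendar year: not in the protocol. Assumed 1.0 for average maturation, with 0.8 to 1.5 as the range.

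**Formulas**
- Raw change = r × t
- Change in (bone age − chronological age) = r × t − t
- Ratio = (r × t) / t = r

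**Results at t = 1, 5 and 10 years**

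| r | Raw change (years) | Bone age − chronological age (years) | Ratio |
|---|---|---|---|
| 0.8 | 0.8, 4.0, 8.0 | −0.2, −1.0, −2.0 | 0.8 |
| 1.0 | 1.0, 5.0, 10.0 | 0, 0, 0 | 1.0 |
| 1.2 | 1.2, 6.0, 12.0 | +0.2, +1.0, +2.0 | 1.2 |
| 1.5 | 1.5, 7.5, 15.0 | +0.5, +2.5, +5.0 | 1.5 |

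At r = 1.2, elapsed time accounts for 5.0 of the 6.0 years at year 5, which is 5.0/6.0 = 83%. At r = 1.5 it is still 5.0/7.5 = 67%.

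**Rate and interval confounded**
- Child A: r = 1.0, t = 1.25; raw change 1.0 × 1.25 = 1.25 years.
- Child B: r = 1.2, t = 1.25/1.2 ≈ 1.04; raw change 1.25 years.
- The raw endpoint gives both the same value. The difference from chronological age gives 0 for A and 1.25 − 1.04 = +0.21 for B. The ratio gives 1.0 and 1.2.

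**Does averaging over patients remove this?** Only in part. With n = 400 and an assumed SD of 0.3 to 1.0 years, the 95% half-width of a mean yearly change is 1.96 × SD/√400, or 0.03 to 0.10 years. Random scatter in timing therefore largely averages out. A shift in the mean interval does not. If nominally yearly assessments were on average 13.2 months apart, average maturation would give 13.2/12 = 1.10 years, the same as a 10% faster rate over an exact year. At 14.4 months it would give 1.20. These intervals are illustrations, not figures from the protocol.

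**The case against.** The strongest reply is that the maturation rate can be recovered. The time frame is yearly, and the change is to be estimated by length of follow-up. Over one exact year, rates of 0.8, 1.0, 1.2 and 1.5 give changes of 0.8, 1.0, 1.2 and 1.5 years. With the precision shown above, a mean excess of 0.2 years would be visible. This stands. A reader might infer that the endpoint measures nothing but time, or that it would hide a real acceleration. The protocol does not support that, because an analyst who sets the change against the true interval can find the rate.

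A reader might also infer that the study has to show whether somapacitan advances skeletal maturation. Section 7 and the objectives in Section 8.2 ask only for a description of changes in clinical parameters. Nor should a between-patient range of assessment intervals be set against a mean drug effect to size the problem, since these are different quantities.

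It can also be said that derivation rules belong in the SAP, which Section 4.10 promises and which is not at hand. That holds for visit windows and similar detail. It does not cover the variable and its unit, which the protocol itself fixes in Table 9-3. Section 9.9 does disclose irregular timing as something to weigh in interpretation, but disclosure does not supply the missing reference.

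Finally, re-expressing the endpoint cannot show that the drug caused an advance. That is correct: the single arm and the lack of a bone-age comparator remain.

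**Conclusion.** The point holds in a limited form. As defined and analysed, the change in bone age is dominated by elapsed time: about +1, +5 and +10 years at 1, 5 and 10 years under average maturation with no drug effect. Under routine-visit timing it does not separate rate from interval. Chronological age is the one benchmark available inside the study, and the endpoint omits it.

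This rests on the assumed rate of one bone-age year per calendar year, on the child still maturing over the period, and on intervals that depart from one year. The extent of that departure is unknown. The endpoint is a descriptive secondary one in a study whose main purpose is long-term safety. The primary endpoint, the sample size and the safety analyses are unaffected.

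**What to change.** In Table 9-3 and Section 9.7.2.2, define the endpoint as one or both of:
- change from baseline in bone age minus chronological age, in years;
- change in bone age divided by change in chronological age between the same two assessments.

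Use the actual assessment dates where the registry holds them. The ratio does not depend on the interval, and the difference shows the accumulated advance or delay. The raw change can stay as a descriptive line. The report should say that, with one arm and no bone-age comparator, an advance cannot be attributed to somapacitan on this evidence alone.

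The cost is a small amount of extra derivation. Section 9.3.3 lists bone age among the variables introduced by "The following baseline characteristics will be available from the GloBE-Reg data", and Section 9.7.2.2 already uses age for subgroups. The protocol does not mention the dates of bone-age assessments, so their availability in GloBE-Reg should be confirmed before the wording is settled.
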